5.5 Post-Procedure to Hospital Discharge

5.5.1 Subject Management

Immediately after the procedure the following will be performed:

1. Heparin or bivalirudin (as market approved by geography) should be discontinued
2. Vascular sheaths should be removed according to standard hospital practice
3. Approved vascular closure devices may be used at the discretion of the Investigator in accordance with the manufacturer's instructions

5.5.2 Clinical and Laboratory Procedures

The following clinical and laboratory procedures will be performed:

1. Qualified study staff at the investigational site will assess the subject's clinical status (including angina) prior to discharge and record any adverse events.
2. Qualified study staff at the investigational site will review the follow-up requirements with the subject to help ensure compliance with the follow-up schedule. Telephone numbers and/or e-mail address should be obtained from the subject to ensure the ability to contact him or her at the required follow-up times. These phone numbers should include all home numbers, work numbers and primary physician numbers. A phone number of a relative or friend should also be requested.

5.5.3 Cardiac Biomarkers

Creatine Kinase (CK) enzyme and troponin will be measured post-procedure following removal of the last catheter as follows:

- 1st draw: >3 hours, <12 hours post procedure
- 2nd draw: >4 hours after 1st draw, <24 hours post procedure

Cardiac enzymes/biomarkers will be collected if they are related to a trial primary or secondary endpoint, including but not limited to death, (suspected) MI or stent thrombosis. These may include creatine kinase (CK) enzyme, creatine kinase myocardial-band (CK-MB) isoenzyme and troponin.

If it is not standard hospital practice to measure CK values, CK-MB values are sufficient. All subjects should have Troponin values.

5.5.4 ECG

A 12-lead ECG will be performed within 24 hours post-procedure or prior to discharge whichever comes first. Additional 12-lead ECGs are required to document any episodes suspicious of cardiac ischemia.

RESOLUTE Onyx 2.0 mm Clinical Study
CONFIDENTIAL - May not be reproduced without written permission from Medtronic

5.6 Follow-Up Requirements

5.6.1 Follow-up General Requirements

The general requirements for follow-up in this trial include:

1. Enrolled subjects who received a study stent will be followed for 3 years after the index procedure by authorized study staff at the investigational site. See [Table 6](#) for follow-up assessment requirements.
2. Subjects in the 2.0 mm Angio subset will return to the site where the procedure was performed for a 13-month clinic visit including an angiogram. Other follow-up contacts will be conducted by telephone, e-mail or clinical visit, unless an unscheduled clinic visit occurs during a follow-up window.
3. A missed follow-up assessment will be documented by the investigator and reported in the eCRF, including the reason for the missed follow-up assessment in the subject's file.
4. Clinical assessments (e.g., angina status, use of antiplatelet medication, new and ongoing adverse events; medical, surgical or dental procedures and the interruption, if any, to antiplatelet therapy) must be performed at each follow-up contact and prior to any interventional procedure (e.g., angiography, PCI) during the 3-year follow-up period.
5. Documentation of referring physicians, general practitioners, cardiologists and family members should be noted to facilitate continued ability to contact a study subject. Any planned long absences by the subject from the area should also be noted.
6. Angiography should be performed for any post-procedure clinical event (e.g., MI) to determine if the event is attributable to the target vessel(s) or a non-target vessel.

The schedule and method for follow-up contacts and windows for each contact is tabled below.

Table 6: Follow-up Contact Requirements

Follow-up Interval	Window	Method*
30 days	± 5 days	Contact
6 months	±14 days	Contact/Clinic Visit**
12 months	± 30 days	Contact
12 month Clinical Follow up must occur at least 1 day prior to the 13 month Angiographic Follow up		
13 months (2.0 mm Angio subset)	± 14 days	Clinic Visit (with Angio)
2 Year	± 30 days	Contact
3 Year	± 30 days	Contact

*Subject contact includes phone call, email or clinic visit

**Clinic visit for subjects with baseline MPI performed, otherwise subject contact visit

5.6.2 Follow-up Data Collection Procedure

The date for the 30-day follow up should be calculated by adding 30 days to the index procedure date (e.g. stent implant on December 5th, 30 day follow-up on January 4th). The dates for the 6 month, 12 month, 13 month and annual (years 2-3) follow-up assessments should be calculated

RESOLUTE Onyx 2.0 mm Clinical Study
CONFIDENTIAL - May not be reproduced without written permission from Medtronic

using the anniversary date of the index procedure (e.g., stent implant on December 5th, 6 month follow-up on June 5th, 12 month and annual thereafter on December 5th). If the procedure was performed on the 31st and the follow-up month has only 30 days, the anniversary should be calculated to the first day of the next month. Visit window calculations will be provided for each subject through the electronic data capture (EDC) system.

Table 7: Subject Follow-up Time Window

Example: Date of implant: 5/DEC/2014

Contact Period	Visit Target Date	Visit Window Dates	
		From	To
30 Day \pm 5 days	4/JAN/2015	30/DEC/2014	9/JAN/2015
6 Month \pm 14 days	5/JUN/2015	22/MAY/2015	19/JUN/2015
12 Month \pm 30 days	5/DEC/2015	5/NOV/2015	4/JAN/2016
13 Month \pm 14 days	5/JAN/2016	22/DEC/2015	19/JAN/2016
2 Year \pm 30 days	5/DEC/2016	5/NOV/2016	4/JAN/2017
3 Year \pm 30 days	5/DEC/2017	5/NOV/2017	4/JAN/2018

5.7 Subject Withdrawal / Removal from the Trial

A trial subject has the right to discontinue participation at any time without penalty or loss of benefits to which the subject is otherwise entitled. A withdrawn subject will be treated according to standard of medical care and will not be replaced. Subjects will be included in the analyses up to the time that consent was withdrawn.

If a subject decides to withdraw from the trial, the investigator will document the reason for withdrawal and indicate any rationale for the withdrawal from the trial in the subject's file. Subjects may decide to withdraw from study follow up visits/contacts but consent to continue to allow data collection from their medical records.

Subject Lost-To-Follow-Up (LTFU) should be avoided as much as possible and investigators are urged to do their utmost best to maintain subject follow-up compliance. Contacting the subject's general practitioner or referring cardiologist should be considered in case the subject cannot be reached in order to obtain information about the subject's health status and documented in the subject's file. Continuous attempts throughout the three year follow-up period should be made to contact the subject, the subject's family or referring physician before documenting a subject LTFU. It is recommended that death study databases (SSDI) should be checked before subjects are considered LTFU.

RESOLUTE Onyx 2.0 mm Clinical Study
CONFIDENTIAL - May not be reproduced without written permission from Medtronic

6.0 BENEFITS AND RISKS

6.1 Benefits

The preclinical data from the Resolute Onyx Stent System to date, in conjunction with the extensive body of pharmacokinetic and clinical data from the Resolute Integrity System, demonstrate that the benefits of the Resolute Onyx Stent System outweigh the risks. There are no guaranteed benefits from participation in the trial. The risks of the Resolute Onyx Stent System are provided below.

6.2 Risks

The risks associated with using this device are those associated with standard percutaneous coronary diagnostic and treatment procedures.

Since the Resolute Onyx Stent System is an investigational device, the risks are not entirely known, but are believed to be similar to those that are associated with the standard, customary stenting of a stenosed coronary artery.

All efforts will be made to minimize these risks by selecting Investigators who are experienced and skilled in interventional procedures including stenting, by clearly defining inclusion/exclusion criteria to ensure only appropriate subjects are enrolled, and by ensuring that treatment and follow-up of the subject are consistent with current medical practices.

6.2.1 Zotarolimus

Subjects' exposure to zotarolimus is directly related to the total amount of stent length implanted. The actual side effects/complications that may be associated with the use of zotarolimus are not fully known.

The adverse events that have been associated with the intravenous injection of zotarolimus in humans include but are not limited to:

- Anemia
- Diarrhea
- Dry Skin
- Headache
- Hematuria
- Infection
- Injection site reaction
- Pain (abdominal, arthralgia, injection site)
- Rash

6.2.2 BioLinx Polymer Coating

The types of risks of the BioLinx polymer coating are expected to be no different than those of other stent coatings. These risks may include but are not limited to the following:

- Allergic reaction

RESOLUTE Onyx 2.0 mm Clinical Study**CONFIDENTIAL - May not be reproduced without written permission from Medtronic**

- Focal inflammation at the site of stent implantation
- Restenosis of the stented artery
- Percutaneous Coronary Diagnostic and Treatment Procedures

6.2.3 Percutaneous Coronary Diagnostic and Treatment Procedures

Other risks associated with using this device are those associated with percutaneous coronary diagnostic (including angiography and IVUS) and treatment procedures. These risks (in alphabetical order) may include but are not limited to the following:

- Abrupt vessel closure
- Access site pain, hematoma or hemorrhage
- Allergic reaction (to contrast, antiplatelet therapy, stent material, or drug and polymer coating)
- Aneurysm, pseudoaneurysm, or arteriovenous fistula (AVF)
- Arrhythmias, including ventricular fibrillation
- Balloon rupture
- Bleeding
- Cardiac tamponade
- Coronary artery occlusion, perforation, rupture, or dissection
- Coronary artery spasm
- Death
- Embolism (air, tissue, device, or thrombus)
- Emergency surgery: peripheral vascular or coronary bypass
- Failure to deliver the stent
- Hemorrhage requiring transfusion
- Hypotension / hypertension
- Incomplete stent apposition
- Infection or fever
- Myocardial infarction (MI)
- Pericarditis
- Peripheral ischemia / peripheral nerve injury
- Renal Failure
- Restenosis of the stented artery
- Shock / pulmonary edema
- Stable or Unstable angina
- Stent deformation, collapse, or fracture
- Stent migration or embolization
- Stent misplacement
- Stroke / transient ischemic attack
- Thrombosis (acute, sub-acute or late)

RESOLUTE Onyx 2.0 mm Clinical Study**CONFIDENTIAL - May not be reproduced without written permission from Medtronic**

7.0 STATISTICAL CONSIDERATIONS

The RESOLUTE ONYX 2.0 mm Clinical Study is a single arm, open label multicenter study enrolling at least 100 subjects with symptomatic ischemic heart disease attributable to stenotic lesions of the native coronary arteries that are amenable to percutaneous treatment with stenting with a Resolute Onyx 2.0 mm stent.

The primary endpoint to be evaluated in this subset is 12 month Target Lesion Failure (TLF) defined as cardiac death, target vessel myocardial infarction (TVMI) (Q wave or non-Q wave), or clinically-driven target lesion revascularization (TLR) by percutaneous or surgical methods.

7.1 Derivation of Performance Goal

The primary safety endpoint of Target Lesion Failure (TLF) at 12 months post-procedure will be compared to a performance goal derived from outcomes of other Drug Eluting Stents (DES).

Since a 2.0 mm DES has not yet been approved in the US or Japan, the TLF rates at 12 months post-procedure with different 2.25 mm DES stents are selected from literature. The weighted average of TLF rate in those stents is 7.9%.

It is expected that a 2.0 mm stent will have a slightly higher TLF rate because smaller lesions will be treated. Therefore, the expected TLF rate for a 2.0 mm DES is 9.4%.

The performance goal is set at 19%, which is approximately 100% above the expected TLF rate for DES 2.0 mm stent subjects.

7.2 Sample Size Justification

If the 12-month TLF rate of the Resolute Onyx 2.0 mm stent is shown to be significantly less than 19%, then the trial will be considered to have met its primary objective. In other words, the assessment of TLF is a testing with the following null and alternative hypotheses:

$$H_0: \pi \geq 19\% \text{ vs. } H_1: \pi < 19\%,$$

where π is the true Resolute Onyx 2.0 mm stent 12-month TLF rate.

The assessment of the null hypothesis will be carried out at the one-sided 0.05 level of significance. Rejection of the null hypothesis indicates the Resolute Onyx 2.0 mm stent 12-month TLF rate is significantly below 19%.

Accounting for a 10% clinical loss to follow-up and one-sided 0.05 level of significance, a sample size of 100 subjects yields more than 80% power to reject the above null hypothesis in favor of the alternative, assuming the true Resolute Onyx 2.0 mm stent 12-month TLF rate is 9.4%.

RESOLUTE Onyx 2.0 mm Clinical Study
CONFIDENTIAL - May not be reproduced without written permission from Medtronic

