1.8 Statistical Methods

The primary safety endpoint of Target Lesion Failure (TLF) at 12 months post-procedure will be compared to a performance goal derived from outcomes of other Drug Eluting Stents (DES). The TLF performance goal of 19% at 12-months is based on US approved 2.25 mm drug-eluting stent data. The RESOLUTE ONYX 2.0 mm Study design with 100 subjects yields more than 80% power, assuming a one-sided type 0.05 level of significance and 10% loss to follow up.

RESOLUTE Onyx 2.0 mm Clinical Study**CONFIDENTIAL - May not be reproduced without written permission from Medtronic**

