4.2 Number of Subjects

At least 100 subjects will be enrolled in the trial.

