6.2. Analysis of the Primary Endpoint

The number and percentage of subjects with 12-month TLF will be presented. A one-sided upper 95% confidence interval of the Resolute Onyx 2.0 mm stent 12-month TLF rate will be calculated through binomial (exact) method. If this upper limit is below 19%, the clinical objective will be considered to have been met.

With regard to clinical outcomes analysis, in subjects receiving treatment of two lesions with a Resolute Onyx 2.0 mm stent, the lesion to be included in the primary analysis, the “analysis lesion”, will be randomly selected at the time of analysis. For subjects receiving treatment of a Resolute Onyx 2.0 mm stent and another size stent, the primary analysis will include the lesion treated with the 2.0 mm stent, regardless of the other stent size. A secondary analysis will be conducted for all target lesions.

The algorithm to randomly select the “analysis lesion” is specified below:

The seed of the ranuni function will be specified in the statistical analysis plan prior to the database lock and will not be changed. Therefore, bias cannot be introduced in the random selection of the lesion in the primary analysis.

A random lesion will be chosen for the primary analysis as follows:

1. Sort the lesions according to patient number and CASS site (with one observation per patient/CASS).
2. Assign a random number to each observation using the SAS ranuni function (the seed will be pre-specified in the statistical analysis plan).
3. Resort the lesions according to patient number and newly created random number.
4. Choose the first patient/CASS observation according to the sort in step 3.

As a supplementary analysis, to account for missing data, subjects who drop out prior to 330 days post-procedure and do not experience TLF will have their 12-month TLF-free status (yes/no) imputed using the multiple imputation, tipping point analysis and worst case analysis.

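### The claim of more than 80% power does not hold for the planned exact binomial test: with 100 enrolled and 10% lost, power at a 9.4% TLF rate is 77.6%

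*Protocol*

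**What the plan says.** Protocol 7.2 sets the null hypothesis that the 12-month TLF rate is at least 19%, tested at one-sided 0.05. It justifies the sample size in one sentence, which opens "Accounting for a 10% clinical loss to follow-up and one-sided 0.05 level of significance" and goes on to say that "a sample size of 100 subjects yields more than 80% power to reject the above null hypothesis in favor of the alternative", at an assumed true rate of 9.4%. SAP 3.3 has the same sentence. The synopsis (Protocol 1.8) says the design "with 100 subjects yields more than 80% power" with the same level and loss, but does not give the 9.4%. None of these places names the formula behind the power figure.

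The analysis method is named. In Protocol 7.4 and SAP 6.2, the one-sided upper 95% limit for the TLF rate "will be calculated through binomial (exact) method", and the objective is met if that limit is below 19%. SAP 6.1 sets the denominator: a subject counts if he or she has had an event by the time point or has follow-up past the lower edge of the visit window. Subjects lost early without an event therefore drop out of it. SAP section 5 plans no interim analysis, so the level is not adjusted.

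**The concern.** Power has to be computed for the test that will be used. An exact binomial limit can be met only at whole numbers of events, so its actual type I error usually lies below the nominal 5%. Its power then tends to be lower than a large-sample formula suggests. With about 90 evaluable subjects, one event more or less in the boundary moves power by almost nine percentage points. A formula that ignores this can land on the wrong side of 80%.

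The sentence matters because it is the only quantitative justification for the size of the trial, and the primary endpoint is the only hypothesis test. The 80% threshold is the sponsor's own. If the figure is wrong, the protocol synopsis, the protocol body and the SAP all understate the risk that a device performing as expected misses its goal.

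**Working it through.** **Inputs, all from the documents**

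- Enrolled: 100 (Protocol 7.2, SAP 3.3)
- Loss to follow-up: 10%, so evaluable n = 100 × 0.90 = 90
- Null rate p0 = 0.19 (Protocol 7.1 and 7.2)
- Assumed true rate p1 = 0.094 (Protocol 7.2)
- Level: one-sided 0.05
- Success: exact one-sided 95% upper limit below 0.19 (Protocol 7.4, SAP 6.2)

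**Step 1. Reproduce the stated figure.** The usual one-sample normal formula, with null variance for the critical value and alternative variance for power, is

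power = Φ{ [p0 − p1 − 1.645·√(p0(1−p0)/n)] / √(p1(1−p1)/n) }

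At n = 90:

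- √(0.19 × 0.81 / 90) = 0.04135, and 1.645 × 0.04135 = 0.06802
- √(0.094 × 0.906 / 90) = 0.03076
- (0.096 − 0.06802) / 0.03076 = 0.909, and Φ(0.909) = 0.818

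This gives 81.8%, in line with the claim. The arcsine formula gives 84.1%. The same normal formula with a continuity correction gives 76.7%, which already falls short.

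**Step 2. Find the exact boundary at n = 90.** The Clopper–Pearson one-sided upper limit for x events is the 95th percentile of a Beta(x+1, n−x) distribution.

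| Events | Upper 95% limit | Below 19%? |
|---|---|---|
| 10/90 | 18.12% | yes |
| 11/90 | 19.42% | no |

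Success therefore needs 10 or fewer events.

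**Step 3. Operating characteristics of that rule.**

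- Type I error: P(X ≤ 10 | n = 90, p = 0.19) = 3.22%
- Power: P(X ≤ 10 | n = 90, p = 0.094) = 77.64%
- Chance of missing the goal at p1: 100 − 77.64 = 22.36%

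**Step 4. Why the two differ.** The normal formula puts the boundary at 0.19 − 0.06802 = 0.12198, or 0.12198 × 90 = 10.98 events. Only whole events occur, so the usable boundary is 10. Allowing an 11th event would give power of 86.3%, but type I error of 6.1%. A score z-test at n = 90 has the same boundary of 10 events, so its true power is also 77.6%.

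**Step 5. Sensitivity.**

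- *Rounding of 9.4%:* true rates of 9.35% and 9.45% give 78.1% and 77.1%. Power of 80% at n = 90 needs a true rate of 9.16%.
- *Random loss:* if each of 100 subjects is lost independently with probability 10%, average power is 78.8%.
- *No loss:* n = 100 gives a boundary of 12 events and power of 85.6%.
- *Other evaluable counts:* exact power is saw-toothed, as shown below.

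| Evaluable n | Boundary (events) | Exact power |
|---|---|---|
| 86 | 10 | 81.7% |
| 87 | 10 | 80.7% |
| 88 | 10 | 79.7% |
| 90 | 10 | 77.6% |
| 92 | 10 | 75.5% |
| 93 | 11 | 83.8% |
| 97 | 11 | 80.1% |
| 98 | 11 | 79.1% |
| 99 | 12 | 86.3% |
| 104 | 12 | 82.2% |

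Every count from 88 to 92 is below 80%, as is 98. Every count checked from 99 upwards is above it.

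**The case against.** The strongest reply is that nobody miscalculated. The power sentence names no method, and a standard large-sample formula gives 81.8% from the stated inputs. On that view the defect is a mismatch between the planning formula and the analysis, not an arithmetic slip. That describes the likely cause fairly. It does not rescue the sentence, because the reader is told what this trial's test will deliver, and this trial's test is exact.

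The second reply is that the gap is small and fragile. It is 2.4 points at 90 evaluable subjects and 1.2 points averaged over random loss. Because power is saw-toothed, losing 13 or 14 of 100 would give more power than losing 10, and losing 3 to 7 also keeps it above 80%. This is true, and it means the figure should not be read to a decimal place. But 10% is the plan's own allowance, and the whole neighbourhood of 88 to 92 falls short.

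Third, 100 is a minimum: "At least 100 subjects will be enrolled in the trial". With 10% random loss, average exact power is 80.0% at 103 enrolled, 80.4% at 104 and 83.1% at 110, so modest over-enrolment would close the gap. That is a real mitigation, but the power sentence is tied to 100 subjects.

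Finally, type I error is protected, and no endpoint, goal or decision rule is affected. That stands. The error concerns the trial's chance of success, not the validity of a success.

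**Conclusion.** The concern holds. Under the planned exact analysis, 100 enrolled subjects with 10% lost give 77.6% power at a true TLF rate of 9.4%, or 78.8% if the loss is treated as random. Neither figure is above 80%. The stated claim is met only by a large-sample approximation that the documents do not name, or by ignoring the loss that the sentence says it allows for.

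The shortfall is about two percentage points, and the test remains conservative, with an actual size of 3.2% at 90 subjects. The result rests on the plan's own inputs and on reading 10% loss as 90 evaluable subjects, which follows from the denominator rule in SAP 6.1 when those lost have had no event.

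**What to change.** In Protocol 1.8, Protocol 7.2 and SAP 3.3, replace the claim with about 78% power for the exact binomial test with 90 evaluable subjects at a true rate of 9.4%, and name the method. State that at 90 evaluable subjects success means at most 10 TLF events. Present this as an illustration of the general rule in Protocol 7.4 and SAP 6.2, since the boundary moves with the evaluable count (10 events at 86 to 92, 11 at 93 to 98, 12 at 99 to 104).

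The cost is a wording change in three places and a slightly less favourable figure. The analysis does not change and no subjects are added.

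If the sponsor prefers to keep the 80% claim, the enrolment target has to support it. Aiming for 93 evaluable subjects (83.8%) is not secure, because power falls back to 79.1% at 98. A floor of 99 evaluable subjects is safe at every count checked above it. With 10% loss that is 99 / 0.90 = 110 enrolled. This step is optional; correcting the stated figure is not.

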7.3 Analysis Populations

Intent-to-Treat (ITT): For this trial, all subjects who sign the written informed consent and also have the study stent (Resolute Onyx 2.0 mm stent) introduced into the guide catheter will be counted in the ITT set, which will be the primary analysis set.

Per-Protocol (PP): The ITT population excluding subjects who do not meet certain key entry criteria. The primary endpoint will also be analyzed in PP population.

